## 9.9 Preliminary Efficacy Analyses

As described in Section 2.2.3, efficacy endpoints include mean change from baseline to Month 3 post-baseline in:

- WRS (performed in quiet)
- QuickSIN-EP and QuickSIN-SF
- SSQ
- SRT
- WIN
- Pure tone audiometry
- DPOAE
- MEMR
- ABR
- ECochG.

Efficacy parameters will be summarized and analyzed separately for the Index Ear and Non-Index Ear using the FAS as the primary population for efficacy analyses. In addition, differences between treatment groups will be calculated as study drug minus Placebo. Change from baseline will be calculated as the value at a follow-up study visit minus the baseline value, where baseline value is defined as the last non-missing measurement recorded prior to initiation of study drug. Summaries of mean change from baseline for each efficacy data will be presented by treatment group and by study visit, as appropriate, with associated 95% confidence intervals.

Exploratory inferential analyses will be conducted to compare efficacy outcomes in subjects assigned to study drug versus those assigned to Placebo. In addition, comparisons of each dose of test drug to Placebo will be conducted. The null hypothesis to be tested is that there is no difference for the efficacy variable between test drug and Placebo with the alternative of a non-zero difference between them. Unless otherwise specified, efficacy parameters will be analyzed using a mixed model with repeated measurements (MMRM) to account for the longitudinal nature of the data. These analyses will include the fixed categorical effect of treatment (PIPE-505 or Placebo) and fixed continuous effect of the baseline value of the efficacy variable. Visit will be treated as the repeated measure, and treatment-by-visit and treatment-by-baseline value interaction terms will be

included. Significance tests will be based on least-squares means using a two-sided  $\alpha = 0.05$ . The primary treatment comparison will be the contrast between treatments at the Month 3 visit.

Supplementary analyses of efficacy data available in the Per-Protocol Set (PPS) will be conducted using the method described above.

## 9.10 Interim Analysis

No interim analysis is planned in this study.

## 9.11 Pharmacokinetic Analyses

[figure not shown]
PK parameters of PIPE-505 will be derived using non-compartmental analysis methods from the concentration-time data for all evaluable subjects. Actual sampling times, rather than scheduled sampling times, will be used in all computations involving sampling times. Table 6 describes the PK parameters that will be determined from concentrations of PIPE-505 in plasma.

**Table 6: Plasma PK Parameters for Analysis**

Parameter	Definition
AUC $_{\infty}$	Area under the plasma concentration-time curve from time 0 to infinity, calculated as $AUC_{\infty} = AUC_{24} + C_{last}/\lambda_z$ , where $C_{last}$ is the last quantifiable concentration.
AUC 24	Area under the plasma concentration-time curve from time 0 to 24 hours, calculated using the linear trapezoidal rule.
C max	Maximum observed plasma concentration.
CL/F	Apparent clearance after extravascular administration, calculated as Dose/AUC $_{\infty}$ after a single dose.
$\lambda_z$	Terminal elimination rate constant, calculated as the negative of the slope of the log-linear regression of the natural logarithm concentration-time curve during the terminal phase.
t 1/2z	Terminal elimination half-life, calculated as $\ln(2)/\lambda_z$ .
t max	Time to reach C max .
V z/F	Apparent volume of distribution during the terminal phase after extravascular administration, calculated as $(CL/F)/\lambda_z$ .

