## SCHEDULE OF EVENTS

Table 2: Schedule of Events

Procedure	Visit	Screening	1	2	3	4	5	6	7
	Day	-56 to -1	0	1	7	14	30	60	90 a
	Window	-	-	-	+/- 2	+/- 2	+/- 3	+/- 7	+/- 7
Informed Consent		X							
Inclusion/Exclusion Criteria		X							
Demographics		X							
Height		X							
Medical and Medication History		X	X						
Physical Examination		X							X
Otological Examination b		X	X	X	X	X	X	X	X
Weight		X							X
Vital Signs c		X	X d	X	X	X	X		X
ECG e		X	X f	X	X				X
FSH g		X							
Pregnancy Test h		X h	X h						X h
Hep B, Hep C, HIV		X							
Urinalysis		X							
Coagulation Panel		X							
Hematology		X	X i	X	X	X	X	X	X
Serum Chemistry		X	X i	X	X	X	X	X	X
PK Blood Collection			X j	X	X	X	X	X	X
Concomitant Medications		X	X	X	X	X	X	X	X
AEs		X	X	X	X	X	X	X	X
Study Drug (PIPE-505) or Placebo Admin			X k						
TRQ		X							X
MoCA		X							
Audiometry (with ultra-high frequency l )		X					X	X	X
DPOAE		X					X		X
ABR/ECochG		X					X		X
Tympanometry		X					X		X
MEMR		X					X		X
SSQ		X							X
WRS		X					X	X	X
SRT		X					X	X	X
QuickSIN-EP (monaural via earphones)		X					X	X	X
WIN (monaural via earphones)		X							X
QuickSIN (binaural via sound field) m		X					X		X

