## Footnotes:

a Subjects who receive study drug and withdraw or are withdrawn from the study early will be requested to complete early termination procedures outlined under Day 90.

b Otological examination will assess the following under direct magnification: external ear, external auditory canal, TM and TM mobility. The otological examinations will be conducted by the unblinded otologist who performs the intratympanic injection and also conducts all post-injection otological examinations through at least Day 30 and preferably throughout the study.

c Vital signs (i.e., blood pressure, pulse rate, respiratory rate, and temperature) will be recorded after subject is at rest in a seated or supine position for at least 5 minutes.

d On Day 0, vital signs will be conducted pre-dose, 30 ( $\pm 5$ ) minutes post-dose, and 4 hours ( $\pm 15$  minutes) post-dose.

e ECG will be recorded after subject is at rest in a supine position for at least 5 minutes.

f On Day 0, ECG will only be conducted at 4 hours ( $\pm 15$  minutes) post-dose.

g FSH level will be obtained on post-menopausal women only (defined as continuous amenorrhea of at least 12 months and not surgically sterile).

h Only female subjects of childbearing potential will require a negative serum pregnancy test at Screening and negative urine pregnancy test prior to randomization at Day 0. Female subjects of childbearing potential will also require a urine pregnancy test at Completion or Early Termination.

i On Day 0, hematology and chemistry lab samples will be collected prior to dosing but do not have to be analyzed prior to dose.

j On Day 0, PK samples will be collected pre-dose and 4 hours ( $\pm 15$  minutes) post-dose.

k The intratympanic injection will be performed by an unblinded otologist who will also conduct all post-injection otological examinations through at least Day 30 and preferably throughout the study.

l Ultra-high frequency audiogram testing [10,000-16,000 Hz] will be performed if available based on site audiometer specifications.

m Sound field binaural testing using a single 0° azimuth loudspeaker.

Approved

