- *In vivo* studies in a murine model of noise-induced hearing loss demonstrated improved ABR thresholds across 3 frequencies (16, 24, and 32 kHz) and mice with 10 dB improvement or more showed a strong trend of an average of 20% or more OHCs after a single intratympanic injection of PIPE-505.

Potential local and systemic toxicity of PIPE-505 (administered both orally and by intratympanic injection) has been tested in Good Laboratory Practice (GLP)-compliant repeat-dose studies in rats, guinea pigs, and monkeys. PIPE-505 was well-tolerated across all of the animal studies, and no systemic or local safety events were observed. In summary, the No Observed Adverse Effect Level (NOAEL) was identified at the local intratympanic dose level of 5.0% in nonclinical studies performed with guinea pigs.

This study will be the first-in-human investigation of PIPE-505, and therefore the pharmacokinetics (PK) and metabolism have not yet been measured in human subjects. Based on nonclinical studies in several different animal species, single unilateral intratympanic administration should result in measurable drug presence within the cochlea perilymph for at least one month after injection. Systemic exposure may primarily result via the Eustachian tube and subsequent absorption through the gastrointestinal route. Nonclinical studies have shown that the amount of systemic exposure following an intratympanic administration is very limited and restricted to within 7 days of drug administration (refer to the IB for a summary of the nonclinical PK studies). Human PK will be assessed based on the collection plan as outlined in the Schedule of Events (SOE) for all subjects dosed with PIPE-505.

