### 2.2.2 Secondary Endpoints

Single dose plasma PK parameters of PIPE-505, including  $AUC_t$ ,  $AUC_{24}$ ,  $AUC_{\infty}$ ,  $C_{max}$ ,  $t_{max}$ ,  $t_{1/2}$ ,  $CL/F$ ,  $V_z/F$ ,  $\lambda_z$ .

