### 9.3 Statistical Analysis Process

Details regarding the statistical methods and definitions will be provided in the Statistical Analysis Plan (SAP). The SAP will serve as a complement to the protocol and supersedes it in case of differences. The SAP will be finalized prior to unblinding to preserve the integrity of the statistical analysis and study conclusions.

All statistical analyses will be performed after the database is locked and unblinded. Statistical analyses will be performed using Version 9.4 or higher of SAS® (SAS Institute, Cary, NC 27513). Summary tables and listings of data will be provided. Summary statistics will be presented by dose group and for all subjects combined as appropriate. For continuous variables, data will be summarized with the number of subjects (N), mean, standard deviation, median, minimum, and maximum by treatment group. For categorical variables, data will be tabulated with the number and proportion of subjects for each category by treatment group.

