2.1. Responsibilities

██████████ will perform the statistical analyses and are responsible for the production and quality control of all tables, figures and listings. Pharmacokinetic (PK) analyses will be carried out by ██████████ ██████████, and the details of analysis are provided in Section 9 of this SAP.

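### Protocol Table 6 builds AUC-infinity on AUC24 instead of AUC_t, so it omits the area between 24 h and the last quantifiable sample

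*Protocol*

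**What the plan says.** Protocol Section 9.11, Table 6, describes AUC-infinity as the area from time 0 to infinity, "calculated as $AUC_{\infty} = AUC_{24} + C_{last}/\lambda_z". In the same row, Clast "is the last quantifiable concentration", with no link to 24 h. The next row defines AUC24 as the area from 0 to 24 h by the linear trapezoidal rule. CL/F is Dose/AUC-infinity and Vz/F is (CL/F)/λz, so both depend on the AUC-infinity formula.

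The Schedule of Events row "PK Blood Collection" marks Day 0 and Days 1, 7, 14, 30, 60 and 90. Footnote j adds: "On Day 0, PK samples will be collected pre-dose and 4 hours" after dosing.

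Protocol Section 2.2.2 ("Single dose plasma PK parameters of PIPE-505, including") lists AUC_t first among the secondary parameters, but Table 6 has no row for it.

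On precedence, Protocol Section 9.3 states: "The SAP will serve as a complement to the protocol and supersedes it in case of differences". SAP Section 2.1 says of the PK work that "the details of analysis are provided in Section 9 of this SAP". In the public copy, SAP Section 9 appears only in the contents list.

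**The concern.** Clast/λz is the extrapolated area from t-last to infinity. It has to be added to the area from 0 to t-last. Table 6 adds it to the area from 0 to 24 h, which leaves a gap whenever t-last is later than 24 h.

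Such samples should be expected in the subjects for whom AUC-infinity is estimated. Only two scheduled post-dose samples (4 h and Day 1) fall at or before a nominal 24 h, so any λz regression on three or more scheduled post-dose samples must reach Day 7 or later. Protocol Section 1.3.1 describes nonclinical systemic exposure as "very limited and restricted to within 7 days of drug administration". That does not rule out a quantifiable sample at the Day 7 visit, which has a window of ±2 days.

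Plasma PK is the only secondary objective of this first-in-human study, and Section 1.4 says the systemic exposure data will inform later designs. AUC-infinity, CL/F and Vz/F are three of the nine listed secondary parameters.

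**Working it through.** **Inputs from the documents.** The formulas are those of Table 6. Nominal post-dose sampling times are 4, 24, 168, 336, 720, 1440 and 2160 h. The plan reports no AUC value to reproduce.

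**Step 1: algebra, no PK assumption.**

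- Consistent formula: AUC-infinity = AUC(0 to t-last) + Clast/λz.
- Table 6: AUC(0 to 24 h) + Clast/λz.
- Difference (Table 6 minus consistent) = −AUC(24 h to t-last) when t-last is after 24 h.

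The difference is zero at t-last = 24 h and negative at any later t-last, whatever value λz takes.

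**Step 2: size for a mono-exponential decline.** The half-lives and the decline model are assumptions. Let C(t) = exp(−λt), so the true area is 1/λ. Then

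Table 6 / true = 1 − exp(−24λ) + exp(−λ·t-last), with λ = ln 2 / half-life.

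With t-last = 168 h (Day 7):

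| Half-life (h) | exp(−24λ) | exp(−168λ) | Table 6 / true | CL/F and Vz/F inflation |
|---|---|---|---|---|
| 12 | 0.250 | 0.0001 | 0.750 | 1.33 |
| 24 | 0.500 | 0.008 | 0.508 | 1.97 |
| 48 | 0.707 | 0.088 | 0.381 | 2.62 |
| 72 | 0.794 | 0.198 | 0.405 | 2.47 |
| 120 | 0.871 | 0.379 | 0.508 | 1.97 |
| 168 | 0.906 | 0.500 | 0.594 | 1.68 |
| 336 | 0.952 | 0.707 | 0.755 | 1.32 |

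The third column is also the fraction of the initial concentration that the assay must still quantify on Day 7 for the case to arise. The 12 h and 24 h rows therefore need a very sensitive assay.

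**Step 3: the same check on sampled data.** Assumptions: one compartment, absorption rate 2/h, samples at 0, 4, 24 and 168 h, the linear trapezoid of Table 6, and λz fitted through 4, 24 and 168 h.

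| Half-life (h) | Table 6 / true | (AUC_t + Clast/λz) / true | AUC_t / true |
|---|---|---|---|
| 12 | 0.72 | 1.79 | 1.79 |
| 24 | 0.47 | 1.54 | 1.53 |
| 48 | 0.357 | 1.190 | 1.101 |
| 72 | 0.388 | 1.079 | 0.879 |
| 120 | 0.498 | 1.020 | 0.639 |
| 168 | 0.587 | 1.006 | 0.505 |

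For half-lives of 12 to 120 h, the Table 6 value is smaller than AUC_t from the same samples. An area from 0 to infinity cannot be smaller than the area from 0 to t-last.

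**Step 4: t-last before 24 h.** If t-last is the 4 h sample and AUC24 is still carried to 24 h, the area from 4 to 24 h is counted twice. The Step 2 formula with t-last = 4 h gives 1.48, 1.58 and 1.54 for half-lives of 4, 8 and 12 h. One scheduled post-dose concentration cannot support a λz regression, so this case is mainly theoretical.

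**The case against.** The strongest reply is that the operative formula cannot be seen. The SAP overrides the protocol, its contents list shows a Section 9.1 on PK parameters and a Section 12 on changes relative to the protocol, and neither text is public. AUC_t is a named endpoint, so a slip confined to one protocol table is plausible. This stands: the error is established for Table 6, not for any reported result.

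Second, t-last may rarely pass 24 h. The Synopsis expects negligible systemic exposure. If Day 7 is below quantification, t-last is Day 1, where nothing is lost at a nominal 24 h, or 4 h, where λz cannot be fitted. Table 6 also sets no three-point minimum for λz. How often the error would occur is therefore unknown. It remains certain for every subject whose λz uses three or more scheduled post-dose samples.

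Third, the correction does not guarantee an accurate AUC-infinity. At half-lives of 12 and 24 h, Step 3 gives 1.79 and 1.54 times the true area after the correction, and at 12 h the corrected value is further from the truth than the printed one. This is also right. The excess comes from applying a linear trapezoid across the gap from 24 to 168 h, which is a separate weakness. It does not make the printed sum valid.

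Fourth, the consequence is limited. No suspension rule or hypothesis test uses AUC-infinity, and the values can be recalculated from stored concentrations. That bears on priority, not on whether the formula is wrong.

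**Conclusion.** The concern holds for the protocol text. Table 6 leaves out exactly the area from 24 h to t-last whenever the last quantifiable sample is later than 24 h. AUC-infinity is then understated relative to AUC_t + Clast/λz, and CL/F and Vz/F are overstated by the inverse factor.

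The direction and the condition are matters of algebra. The size is hypothetical. Under mono-exponential decline with t-last on Day 7, the loss is 25% to 62% of the true area over assumed half-lives of 12 to 336 h, and the inflation of CL/F and Vz/F is 1.3- to 2.6-fold. Cmax, tmax, AUC24, λz, t1/2 and the primary safety endpoint are not affected. It should be fixed before PK parameters are reported. Whether results would actually be affected depends on SAP Section 9.1.

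**What to change.** Add a row to Table 6 defining AUC_t as the area from time 0 to the last quantifiable concentration, and change the AUC-infinity row to AUC_t + Clast/λz.

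Before PK parameters are reported, confirm that SAP Section 9.1 uses the same formula. If it does, correct the protocol wording or record the difference in SAP Section 12. If it repeats Table 6, correct both documents.

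The cost is one definition, one changed term and one cross-check, with no extra samples, visits or subjects. The choice of trapezoidal rule over the sparse late samples and the minimum number of points for λz deserve their own decision, but this correction does not depend on them.

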## 9.12 Sample Size Calculation and Power Considerations

The planned sample size of 24 subjects (18 Active and 6 Placebo) is not based on statistical considerations but is expected to be sufficient to categorize initial safety, tolerability, and PK characteristics of PIPE-505.

**Table 7:**

A large rectangular area of the page has been completely redacted with black bars.

	[Redacted]								
	■	■	■	■	■	■	■	■	■
	■	■	■	■	■	■	■	■	■
	■	■	■	■	■	■	■	■	■
	■	■	■	■	■	■	■	■	■
	■	■	■	■	■	■	■	■	■
	■	■	■	■	■	■	■	■	■
	■	■	■	■	■	■	■	■	■
	■	■	■	■	■	■	■	■	■
	■	■	■	■	■	■	■	■	■

## 10. SPONSOR'S AND INVESTIGATOR'S RESPONSIBILITIES

This study is conducted in accordance with current applicable US regulations, International Conference on Harmonisation Guidelines (ICH) GCP Guidelines, and local ethical and legal requirements.

### 10.1 Sponsor's Responsibilities

#### 10.1.1 Good Clinical Practice Compliance

The study Sponsor and designees will undertake their assigned roles for this study in compliance with all applicable industry regulations and ICH Good GCP Guideline E6(R2) (2018).

Visits to sites are conducted by representatives of the study Sponsor or designee to inspect study data, subjects' medical records, and CRFs in accordance with current GCP and the respective local and inter/national government regulations and guidelines. Records and data may additionally be reviewed by auditors or by regulatory authorities.

The Sponsor ensures that Local Regulatory Authority requirements are met before the start of the study. The Sponsor (or a nominated designee) is responsible for the preparation, submission, and confirmation of receipt of any Regulatory Authority approvals required prior to release of IP for shipment to the site.

#### 10.1.2 Public Posting of Study Information

The Sponsor is responsible for posting appropriate study information on applicable websites. Information included in clinical study registries may include participating Investigators' names and contact information.

#### 10.1.3 Study Suspension, Termination, and Completion

The Sponsor may suspend or terminate the study or part of the study at any time for any reason. If the study is suspended or terminated, the Sponsor will ensure that applicable regulatory agencies and IRBs are notified as appropriate. Additionally, the discontinuation of a registered clinical study which has been posted to a designated public website will be updated accordingly.

### 10.2 Investigator's Responsibilities

#### 10.2.1 Good Clinical Practice Compliance

The Investigator must undertake to perform the study in accordance with ICH GCP Guideline E6(R2) (2018), and applicable regulatory requirements and guidelines.

It is the Investigator's responsibility to ensure that adequate time and appropriately trained resources are available at the site prior to commitment to participate in this study. The Investigator

should also be able to estimate or demonstrate a potential for recruiting the required number of suitable subjects within the agreed recruitment period.

The Investigator will maintain a list of appropriately qualified persons to whom the Investigator has delegated significant study-related tasks. *Curriculum vitae* for Investigators and sub-investigators are provided to the study Sponsor (or designee) before starting the study.

### **10.2.2 Protocol Adherence and Investigator Agreement**

The Investigator and any co-investigators must adhere to the protocol as detailed in this document. The Investigator is responsible for enrolling only those subjects who have met protocol eligibility criteria. Investigators are required to sign an Investigator Agreement to confirm acceptance and willingness to comply with the study protocol.

If the Investigator suspends or terminates the study at their site, the Investigator will promptly inform the Sponsor and the IRB and provide them with a detailed written explanation. The Investigator will also return all IP, containers, and other study materials to the Sponsor. Upon study completion, the Investigator will provide the Sponsor, IRB, and regulatory agency with final reports and summaries as required by (inter)national regulations.

Communication with local IRBs, to ensure accurate and timely information is provided at all phases during the study, may be done by the Sponsor or designee, Investigator, or for multi-site studies, the Coordinating Investigator according to national provisions and will be documented in the Investigator Agreement.

### **10.2.3 Documentation and Retention of Records**

#### *10.2.3.1 Case Report Forms*

Access to the eCRFs will be provided by the Sponsor or designee and should be handled in accordance with instructions from the CRO.

The Investigator is responsible for maintaining adequate and accurate medical records from which accurate information is recorded onto eCRFs, which have been designed to record all observations and other data pertinent to the clinical investigation.

All data sent to the Sponsor must be endorsed by the Investigator.

The Clinical Research Associate (CRA)/Study Monitor will verify the contents against the source records. If the data are unclear or contradictory, queries are sent for corrections or verification of data.

#### *10.2.3.2 Recording, Access, and Retention of Source Data and Study Documents*

Original source documents to be reviewed during this study may include, but are not limited to, questionnaires, laboratory reports, ECG tracings, x-rays, radiologist reports, or reports,

photographs, clinic notes or pharmacy records and any other similar reports or records of any procedure performed in accordance with the protocol. Source documents may also include CRFs or electronic devices when information is recorded directly onto such forms or devices.

Whenever possible, the original recording of an observation should be retained as the source document; however, a photocopy is acceptable provided that it is a clear, legible, and exact duplication of the original document.

All key data must be recorded in the subject's medical records.

The Investigator must permit authorized representatives of the Sponsor, the respective national, local, or foreign regulatory authorities, the IRB, and auditors to inspect facilities and to have direct access to original source records relevant to this study, regardless of media.

The CRA/Study Monitor (and auditors, IRB or regulatory inspectors) may check the eCRF entries against the source documents. The consent form includes a statement by which the subject agrees to the monitor/auditor from the Sponsor or its representatives, national or local regulatory authorities, or the IRB having access to source data (e.g., subject's medical file, appointment books, original laboratory reports, etc.).

These records must be made available within reasonable times for inspection and duplication, if required, by a properly authorized representative of any regulatory agency (e.g., the US Food and Drug Administration [FDA], European Medicines Agency [EMA], UK Medicines and Healthcare Products Regulatory Agency [MHRA]) or an auditor).

Essential documents must be maintained according to ICH GCP requirements and may not be destroyed without written permission from the Sponsor.

